4.5 Treatment masking

All study personnel and subjects will be masked for the duration of the study until the last subject completes follow-up assessments. The University of Pennsylvania Research Pharmacist, the unblinded statistical analyst, and the DSMB will be unmasked; the Research Pharmacist will supply the DSMB and the identified biostatistician with the drug/placebo identifier. This review will occur only in a closed meeting.

4.6 Drug Logistics and Accountability

Each Field Center will have a supply of study drug kits including vitamin D supplements, which will be replenished by the University of Pennsylvania Research Pharmacy as they are dispensed to study subjects. All study drugs dispensed to the Field Centers will be stored in accordance with Good Clinical Practice (GCP) and Good Manufacturing Practices (GMP) requirements and the instructions given by the clinical supplies department of the Institution and will be inaccessible to unauthorized personnel.

4.6.1 Accountability

The field center investigator, or a responsible party designated by the investigator, must maintain a careful record of the inventory and disposition of the investigational agent using the drug accountability form.

4.6.2 Destruction and Return

At the end of the study, unused supplies of AN should be destroyed according to institutional policies. Destruction will be documented in the drug accountability record.

Chapter 5. Data Collection

5.1 Study Visits and Contacts

5.1.1 Informed Consent

Potentially eligible subjects will be referred if there is interest in enrolling. The following procedures will be performed during the screening process:

- Sign and date the informed consent and HIPAA release
- Review of inclusion/exclusion criteria

Subjects will be permitted to provide verbal consent for screening over the phone. A consent script will be provided and documentation of verbal consent will be noted. After the subject has consented, the subject will be scheduled for a screening visit within 60 days if the subject meets inclusion/exclusion criteria thus far. The research coordinator will call the subject 1-2 days prior to the screening visit and send a reminder letter as well if the screening visit is not conducted within the 2 weeks following consent. Subjects will be asked if they have had any of the following tests within 7 days of their scheduled screening visit (Barium enema, Upper GI X-ray series, Lower Gi X-ray series, Nuclear medicine scan, or other test using contrast (dye) or radioactive materials. If the answer is “yes” then the subject should be rescheduled for the screening visit as the DXA will not be able to be performed. If the subject has not had the above tests within 7 days of the scheduled visit, subjects will be instructed to take their routine medications on the morning of the visit and to bring their medications to the visit. When the subject arrives for the screening visit, written study consent will be obtained if it has not already been obtained.

5.1.2 Screening

The subject will arrive at the study site outpatient facility. The following procedures will be performed:

- Review medical history
- Review current medications
- WHO functional class
- Vital signs
- Clinical Labs/Phlebotomy: complete blood count, including hemoglobin, hematocrit, and platelet count, clinical chemistries, liver function tests, coagulation studies, FSH (in women only, without oophorectomy or women > 50 yrs who have not menstruated during the preceding 12 months), and calcium
- DXA scan
- Provide instructions on recording of new medications and dose changes
- Instruct subjects to bring routine medications to baseline visit, do not eat or drink (except water) 12 hours before baseline visit, and to avoid smoking and heavy exercise for 12 hours before the baseline visit

Clinical labs will be processed internally at each Field Center. After consent and screening visit, the subject will be scheduled for a baseline study visit within 28 days at the Field Center. The research coordinator will call the subject and the PAH clinician 24 hours after the study visit if laboratories results were abnormal and clinically significant.

5.1.3 Study Day – Visit 1 (Baseline)

The research coordinator will call the subject 1-2 days before the visit as a reminder. The coordinator will instruct the subject to not eat or drink (except water) and to avoid heavy exercise for 12 hours before the study day assessment. The coordinator will also request that the subject refrain from smoking for 12 hours prior to the study visit. Subjects will be instructed to take their routine medications on the morning of the visit and to bring any new medication to the visit for review. Subjects will also be instructed to bring a snack with them to the visit to eat at the center after blood draw.

Baseline information will be used to characterize the participants and to compare the experimental groups with regards to demographics and other variables. Safety laboratories and DXA bone density results obtained at the screening visit will be used as baseline measurements. Eligibility criteria will be confirmed prior to randomization to treatment group.

The subject will arrive at the study site outpatient facility. The following procedures will be performed:

- Complete SF-36, emPHasis-10
- Urine collection
- Phlebotomy/Research laboratories
- Eat a small snack
- Interim medical history
- Review current medications
- WHO functional class assessment
- Vital signs
- Physical exam
- Review of inclusion/exclusion criteria
- Six minute walk testing with Borg scores
- Echocardiography
- Randomization to treatment group
- Provide actigraph, diary, and instructions
- Dispense supply of study drug, vitamin D supplement, and provide instructions
- Reinforce instructions on recording of new medications and dose changes
- Reinforce instructions on bringing the study medications to all visits

Urine sample and blood samples for study assays will be processed and banked at site for later shipment. After fasting research labs have been drawn, the subject will have the opportunity to eat a snack. The subject will complete the SF36 and emPHasis-10. The investigator or research nurse will take a history/interim history and perform a physical

examination including checking vital signs, and review current medications. The subject will perform the six minute walk test (6MWT). Echocardiography will be performed.

All screening laboratory tests must be received and all inclusion/exclusion criteria confirmed by an investigator before the subject can be formally randomized. The subject will be randomized to a treatment group using a web-based database. A pre-packaged 6 month supply of study medication (AN 1 mg or placebo) will be given to the subject. The subject will be instructed to take one tablet in the morning once each day with or without food starting **eight days after the baseline visit** (i.e., if the baseline visit is on a Tuesday, the subject should start study mediation the Wednesday of the next week). The subject will also be provided with a Vitamin D supplement to begin taking concurrently with the study medication. Subjects will receive dietary counselling about maintaining adequate calcium intake (1200 mg each day).

Following this, the research coordinator will provide the patient with the actigraph equipment and activity diary. Thorough instructions will be given to subjects on the use of the actigraph equipment and the activity diary. Subjects will be instructed to begin wearing the actigraph the day after the baseline visit. The subject will be asked to continue wearing the device for 7 days and complete the activity diary for these 7 days. Subjects will be given a prepaid envelope to return the actigraph and activity diary after the seven days. Subjects will start study drug on the day after the last day of wearing the actigraph.

Once all procedures are complete and study drug, vitamin supplement, actigraph instructions and diary are provided, the research coordinator will thank the subject for his/her attendance and reinforce compliance with the study medication and protocol. The subject's primary PAH physician and medical doctor will be alerted to the subject's participation in the clinical trial.

The research coordinator will call the subject on the morning of study day 8 after this visit to remind the subject to return the actigraph device and to begin taking the study medication and Vitamin D supplement.

Note: For male participants or female participants who have been clinically documented as post-menopausal [i.e. (1) > 50 years old and have not menstruated during the preceding 12 months or (2) have undergone bilateral oophorectomy], the screening and baseline visits may be combined, as long as the DXA results and laboratory results can be made immediately available. Review of medical history, medications, and informed consent must be obtained prior to the combined visit.

5.1.4 Study Day - Visit 2 (Month 3 ± 14 days)

The research coordinator will ship the actigraph and activity diary to the subject and call the subject 12 days before the visit as a reminder to start wearing the actigraph 7 days before the visit. The coordinator will review the instructions on how to use the actigraph and how to complete the activity diary during this phone call. The research coordinator will call again 1-2 days before the visit to remind the subject of his/her appointment. The

coordinator will instruct the subject to not eat or drink (except water) and to avoid heavy exercise for 12 hours before the study day assessment. The coordinator will also request that the subject refrain from smoking for 12 hours prior to the study visit. Subjects will be instructed to take their routine medications on the morning of the visit and to bring any new medications, the study drug, a snack, the actigraph, and the activity diary with them to the visit.

The subject will arrive at the study site outpatient facility. The following procedures will be performed:

- Complete SF-36, emPHasis-10
- Phlebotomy/Research laboratories
- Interim medical history/symptom assessment
- Review current medications
- WHO functional class assessment
- Vital signs
- Physical exam
- Six minute walk testing with Borg scores
- Review of adverse events
- Study drug accountability
- Collect the actigraph and activity diary
- Reinforce instructions on recording of new medications and dose changes
- Reinforce instructions on bringing the subject's study medications to all visits
- Reinforce instructions on actigraphy use and activity diary completion

The subject will complete the SF36 and emPHasis-10. Blood samples for study assays will be processed and banked at site for later shipment.

The investigator or research coordinator will take an interim history and perform a physical examination including vitals, review current medications, perform a pill count, and assess side effects.

The subject will perform the six minute walk test (6MWT).

The research coordinator will thank the subject for their attendance and reinforce compliance with the study medication and protocol.

5.1.5 Study Day – Visit 3 (Month 6 ± 14 days)

The research coordinator will ship the actigraph and activity diary to the subject and call the subject 12 days before the visit (and 7 days before the visit) as a reminder to start wearing the actigraph 7 days before the visit and will call again 1-2 days before the visit as a reminder. The coordinator will instruct the subject to not eat or drink (except water) and to avoid heavy exercise for 12 hours before the study day assessment. The coordinator will also request that the subject refrain from smoking for 12 hours prior to the study visit. Subjects will be instructed to take their routine medications on the

morning of the visit and to bring any new medications, study drug, a snack, the actigraph and activity diary with them to the visit.

The subject will arrive at the study site outpatient facility. The following procedures will be performed:

- Complete SF-36, emPHasis-10
- Phlebotomy/Research laboratories
- Urine collection
- Eat a small snack
- Interim medical history/symptom assessment
- Vital signs
- Review current medications
- WHO functional class assessment
- Physical exam
- Study drug accountability
- Dispense study drug & vitamin D supplement and reinforce instructions
- Six minute walk testing with Borg scores
- Echocardiogram
- Collect actigraph and activity diary
- Reinforce instructions on recording of new medications
- Reinforce instructions on bringing the subject's routine and study medications to the follow-up visit
- Reinforce instructions on actigraphy use and activity diary completion

The subject will complete the SF36 and emPHasis-10 questionnaires. Urine sample and blood samples for study assays will be processed and banked at site for later shipment. After the fasting research blood sample is obtained, the subject will be given the opportunity to eat a small snack.

The investigator or research coordinator will take an interim history and perform a physical examination including vitals, review current medications, perform a pill count, dispense a new bottle of study medication, and assess side effects.

The subject will perform the 6MWT. Echocardiography will be performed.

The research coordinator will thank the subject for their attendance and reinforce compliance with the study medication and protocol.

5.1.6 Phone Call (Month 9 ± 14 days)

The research coordinator will call the subject. Symptoms and potential side effects will be assessed and changes in medications will be reviewed/recorded. Medication compliance will be assessed and reinforced.

5.1.7 Study Day – Visit 4 (Month 12 ± 14 days)

The research coordinator will ship the actigraph and activity diary to the subject and call the subject 12 days before the visit (and 7 days before the visit) as a reminder to start wearing the actigraph 7 days before the visit and will call again 1-2 days before the visit as a reminder. The coordinator will instruct the subject to not eat or drink (except water) and to avoid heavy exercise for 12 hours before the study day assessment. The coordinator will also request that the subject refrain from smoking for 12 hours prior to the study visit. Subjects will be instructed to take their routine medications on the morning of the visit and to bring any new medications, study drug, a snack, the actigraph and activity diary with them to the visit.

The subject will arrive at the study site outpatient facility. The following procedures will be performed:

- Complete SF-36, emphasis-10
- Phlebotomy/Research laboratories
- Eat a small snack
- Interim medical history/symptom assessment
- Review current medications
- WHO functional class assessment
- Vital signs
- Physical exam
- Six minute walk testing with Borg scores
- Echocardiogram
- Complete DXA scan
- Study drug accountability
- Collect actigraph and activity diary

The subject will complete the SF36 and emPHasis-10. Research blood samples for study assays will be processed and banked at site for later shipment. After the fasting research blood draw, the subject will have the opportunity to eat a snack.

The investigator or research coordinator will take an interim history and perform a physical examination including vitals, review current medications, and assess side effects.

The subject will perform the 6MWT. Echocardiography and a DXA bone density scan will be performed.

The research coordinator will thank the subject for their participation in the study.

5.1.8 Telephone follow-up (Week 54)

The research coordinator will call the subject approximately 2 weeks after the Month 12 visit. Symptoms and potential ongoing side effects after stopping study drug will be

assessed. The research coordinator will once again thank the subject for participation in the study.

5.2 Study schedule of endpoints & procedures

The table below summarizes the study endpoint assessments and procedures.

Table 1. Study Procedures

	Consent	Screening*	Baseline	Month 3	Month 6	Month 9	Month 12	Week 54
Visit #			1	2	3		4	
Telephone Call #						1		2
Day#		within 60days of Consent	- 28- 0	90 ± 14	182 ± 14	272 ± 14	365 ± 14	380 ± 7
Informed consent	X							
History and physical exam								
Medical history		X						
Symptom assessment			X	X	X	X	X	X
Medications		X	X	X	X	X	X	X
Vital signs		X	X	X	X		X	
Physical exam			X	X	X		X	
WHO functional class		X	X	X	X		X	
Testing								
Phlebotomy		X	X	X	X		X	
CBC w differential, Chemistry, LFTs, PT/INR		X						
FSH (women only)		X						
NT-proBNP, sex hormones and other research labs)			X	X	X		X	
DXA		X					X	
Six minute walk test			X	X	X		X	
SF-36, emPHasis-10			X	X	X		X	
Echocardiogram			X		X		X	
Actigraphy			X	X	X		X	
Urine collection			X		X			
Study procedures								
Dispense study drug/placebo & vitamin supplements			X		X			
Adverse events			X	X	X	X	X	X
Medication compliance				X	X	X	X	

* For male participants or female participants who have been clinically documented as post-menopausal [(1) > 50 years old and have not menstruated during the preceding 12 months or (2) have undergone bilateral oophorectomy], the screening and baseline visits may be combined, as long as the DXA results and laboratory results are immediately available. Review of medical history, medications, and informed consent must be obtained prior to the combined visit.

5.3 Remote Study Visits (RSVs)

Remote Study Visits (RSVs) may be performed instead of in-person visits while restrictions are in place during the COVID-19 pandemic. Screening and Baseline visits (Visit 1) cannot be performed as RSVs. All visits will be conducted by phone or web-meeting software in a private space to ensure subject confidentiality.

Prior to the RSV:

The research coordinator will mail the SF-36 and emPHasis-10 questionnaires, actigraph, activity diary, and six minute walk materials (surveyor's wheel/tape measure, flat markers to denote track length, pulse oximeter, timer if needed, Borg Score Card and 6MWT instructions) to the subject prior to the start of the visit window. The research coordinator will also call the subject at this time to remind the subject to start wearing the actigraph 7 days before the phone visit. During this call, the coordinator will review the instructions on how to use the actigraph and how to complete the activity diary. The research coordinator will review instructions on how to perform the 6MWT and schedule with the subject when the walk will be performed. The PI (or Nurse Practitioner/physician study delegate as recorded on the Delegation of Authority Log) will confirm if the subject is medically stable to perform the 6MWT. The research coordinator will call again 1-2 days before the visit to remind the subject of his/her phone or teleconference appointment.

The study PI (or appropriate delegate) will contact the subject to complete an abbreviated physical exam (by video if possible, such as to assess for edema), complete WHO functional class, and review common symptoms associated with anastrozole. The PI will then confirm with the research coordinator if the subject is able to perform the 6MWT remotely. This PI assessment may occur at any time during the visit window, but should be performed prior to the remote 6MWT.

The subject can perform the 6MWT any day during the visit window following the PI assessment. The subject will schedule the 6MWT with the research coordinator to aid in executing the remote walk. The subject must have a companion that can assist with the remote walk in order for the remote walk to be performed. A wearable device ("wristwatch") utilizing the Global Positioning System (GPS) to record distance may be supplied to be worn during the walk test along with a downloadable application for a smartphone. Subjects who perform a remote walk will also be scheduled to do an in-person six minute walk test if restrictions in place are lifted within the visit window.

During the RSV:

- Review SF-36, emPHasis-10
- Review current medications
- Abbreviated vital signs
- Review of adverse events
- Study drug accountability
- Review the actigraph and activity diary
- Reinforce instructions on recording of new medications and dose changes

- Reinforce instructions on how to take study medication and to not throw away any empty/used medication bottles
- Review instructions for 6MWT, if not already performed

The study coordinator will call the subject at the scheduled time. The subject will complete the SF-36 and emPHasis-10 questionnaires on the same day as the phone call. The study coordinator will review answers to questionnaires and enter data in the database. If the questionnaires were not completed, the research coordinator may also administer the questionnaires over the phone.

The research coordinator will take an interim medical history, review current medications, perform a pill count with the subject counting the number of pills left in the bottle, and assess side effects. Study drug will be shipped directly to the subject when needed.

The research coordinator will have the subject assess vital signs using the study-provided pulse oximeter and blood pressure cuff if available. The subject will weigh himself or herself. The values will be read (or shown if videoconferencing) to the coordinator and recorded.

The research coordinator will schedule an in-person visit at the center if the center is re-opening within the allowable visit window. The research blood draw, echocardiography, six minute walk test, and DXA will be done in-person. A visiting health service may be utilized to collect research blood and/or urine if the subject agrees. The research coordinator will thank the subject for their compliance with the RSV and reinforce compliance with the study medication and protocol.

Study Drug for Remote Study Visits

Study drug and Vitamin D may be mailed to subjects if an in-person 6 Month Visit cannot be scheduled.

Additional study drug up to six weeks (42 pills) and vitamin D may be mailed to subjects at the 12 Month Visit if an in-person visit can be scheduled within 16 weeks of the Visit 4 study window due to the center re-opening for subject visits.

Week 54 Phone Call

The Week 54 Phone Call should be completed 7-10 days after the last study assessment that is scheduled for the RSV Month 12 Visit.

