**Pulmonary Hypertension and Anastrozole Trial
(PHANTOM)
Protocol**

June 17, 2020

Version 4.2

NCT03229499

**[name], MS
Perelman School of Medicine at the
University of Pennsylvania
Principal Investigator**

Protocol Summary

OBJECTIVES:

The primary objectives of this study are to determine whether anastrozole (AN) may improve six minute walk distance (6MWD) at six months compared to placebo and to assess safety and side effects up to twelve months in pulmonary arterial hypertension (PAH).

Secondary objectives include:

- To assess the effect of AN vs. placebo on 6MWD at additional time points (three months and twelve months).
- To assess the effect of AN vs. placebo on right ventricular (RV) function at six months and twelve months.
- To assess the effect of AN vs. placebo on plasma NT-proBNP level and other biomarkers at three months, six months and twelve months.
- To assess the effect of AN vs. placebo on the SF36 and emPHasis-10 at three months, six months and twelve months.
- To assess the effect of AN vs. placebo on actigraphy-measured physical activity at three months, six months and twelve months.
- To assess the effect of AN vs. placebo on the time-to-clinical worsening (TTCW) at twelve months.
- To assess the effect of AN vs. placebo on bone mineral density at twelve months.

STUDY DESIGN:

Multi-center, randomized, double-blind, placebo-controlled, Phase II study of 84 subjects with PAH. Eligible subjects will be randomly assigned to receive either AN or placebo for twelve months.

STUDY POPULATION:**Inclusion criteria:**

- Previous documentation of mean pulmonary artery pressure > 25 mm Hg with a pulmonary capillary wedge pressure (or left ventricular end-diastolic pressure) < 16 mm Hg and PVR > 3 WU at any time before study entry.
- Diagnosis of PAH which is idiopathic, heritable, drug- or toxin-induced, or associated with connective tissue disease, congenital heart disease, portal hypertension, or HIV infection and receiving treatment for PAH.
- Most recent pulmonary function tests with FEV1/FVC $> 50\%$ AND either a) total lung capacity $> 70\%$ predicted or b) total lung capacity between 60% and 70% predicted with no more than mild interstitial lung disease on computerized tomography scan of the chest.
- Ability to perform six minute walk testing without significant limitations in musculoskeletal function or coordination.
- If female, post-menopausal state, defined as:

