 - > 50 years old and a) have not menstruated during the preceding 12 months or b) have follicle-stimulating hormone (FSH) levels (> 40 IU/L) **or**
 - < 50 years and FSH (> 40 IU/L) **or**
 - having had a bilateral oophorectomy.
- Informed consent.

Exclusion criteria:

- Current treatment with estrogen, hormone therapy, or anti-hormone therapy (tamoxifen, fulvestrant, etc.)
- WHO Class IV functional status.
- History of invasive breast cancer.
- Clinically significant untreated sleep apnea.
- Left-sided valvular disease (more than moderate mitral valve stenosis or insufficiency or aortic stenosis or insufficiency), pulmonary artery or valve stenosis, or ejection fraction < 45% on most recent echocardiography (within 1 year).
- Initiation of PAH therapy (prostacyclin analogues, endothelin-1 receptor antagonists, phosphodiesterase-5 inhibitors, riociguat, selexipag) within three months of enrollment; the dose must be stable for at least three months prior to Baseline Visit. PAH therapy which is stopped and then restarted or has dose changes which are not related to initiation and uptitration will be allowed within 3 months prior to the Baseline Visit.
- Hospitalized or acutely ill.
- Renal failure (creatinine \geq 2.0).
- Hypercalcemia (\geq Grade 2 per NCI-CTCAE v4.0).
- Severe osteoporosis:
 - T score -2.5 to -3.4 without bone modifying treatment OR T score = -3.5 or lower
- Child-Pugh Class C cirrhosis.
- Current or recent (< 3 months) chronic heavy alcohol consumption.
- Enrollment in a clinical trial or concurrent use of another investigational drug or device within 30 days of screening visit.
- Age < 18.

PRIMARY ENDPOINT:

- Difference in changes in distance walked in six minutes between AN and placebo groups at six months.

SECONDARY ENDPOINTS:

- Difference in 6MWD between AN and placebo groups at three and twelve months.
- Difference in right ventricular function between AN and placebo groups at six months, and twelve months.
- Difference in changes in plasma NT-proBNP level and other biomarkers between AN and placebo groups at three months, six months and twelve months.
- Difference in changes in SF36 and emPHasis-10 between AN and placebo groups at three months, six months and twelve months.
- Difference in changes in actigraphy-measured physical activity between AN and placebo groups at three months, six months and twelve months.
- Difference in time-to-clinical worsening (TTCW) between AN and placebo groups at twelve months.

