4.2 Placebos and study drug packaging

AN and placebo tablets will be repackaged by the Research Pharmacy at the University of Pennsylvania Medical Center. At the Research Pharmacy, capsules will be packaged (100 tablets each) into white HDPE pharmaceutical vials with a tamper-evident liner and child-resistant cap. Bottles will be fully labeled to meet state and FDA requirements, and packaged into labeled kits. There will be two bottles (6 month supply) of drug product dispensed to study subjects at the baseline study visit and at the 6 month visit during the treatment phase. Study drug must be stored at room temperature and protected from moisture. Subjects will be asked to bring bottles at the 3-month, 6-month, and 12-month visits to allow for tracking of adherence and medication control. At the end of the study, after accountability has been completed and notification by the Clinical Coordinating Center (CCC) has been sent, study product can be destroyed at each Field Center's Research Pharmacy.

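### After a remote Month-12 visit, clinic measurements may follow up to 16 weeks later while extra study drug is capped at 42 pills, so some may be taken after the drug has run out

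*Combined protocol and SAP*

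**What the plan says.** The Protocol Summary sets the treatment period: "Eligible subjects will be randomly assigned to receive either AN or placebo for twelve months". Among the secondary endpoints it lists "Difference in 6MWD between AN and placebo groups at three and twelve months", and RV function, NT-proBNP and other biomarkers, and bone density also at twelve months.

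During COVID-19 restrictions Section 5.3 allows remote visits after baseline. For a remote Month-12 visit it provides: "Additional study drug up to six weeks (42 pills) and vitamin D may be mailed to subjects at the 12 Month Visit". The condition is "if an in-person visit can be scheduled within 16 weeks of the Visit 4 study window". Table 2 in Section 5.4 repeats the 42-pill limit in note 5. Note 3 allows the Month-12 research blood, in-clinic walk test and echocardiogram within 16 weeks of the remote visit. Note 4 gives the same 16 weeks for DXA but permits it later.

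Chapter 7 says nothing on visit windows or on values obtained after study drug has ended. Section 7.3.1 includes all randomized subjects. Section 7.3.5 supports continued follow-up of subjects who stop drug or have a serious adverse event.

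**The concern.** The extension exists to bridge the wait for a delayed clinic visit, yet it is shorter than the wait that the same sentence allows. A subject can follow every instruction, take every tablet supplied, and still be measured for Month 12 with no drug left. This differs from the case that Section 7.3.5 argues for: the subject has not chosen to stop, and no adverse event has intervened. Treatment has ended by schedule, and the schedule then places the measurement afterwards.

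Three things are at stake.

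- **The 12-month contrasts.** If the effect wanes after the last dose, off-drug values pull the anastrozole–placebo difference toward zero for RV function, in-clinic walk distance and any delayed biomarkers. Section 2.2 values the twelve-month follow-up partly for its added patient-time on study drug.
- **Harmonization of remote walks.** Section 6.1.1 uses later clinic walks to harmonize the remote ones. At Month 12 that can pair an on-drug remote walk with an off-drug clinic walk, which mixes test setting with drug status.
- **Safety follow-up.** Section 9.6.3 ends adverse event follow-up 14 days after the last dose and identifies that point with the Week 54 call. Section 5.3 and Table 2 tie the call to 7–10 days after the last assessment. If drug ends well before that assessment, both cannot hold.

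**Working it through.** **Inputs**

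- Dosing (Section 5.1.3): the subject is to "take one tablet in the morning once each day with or without food starting" "eight days after the baseline visit". That is 1 tablet a day with the first dose on day 8.
- Regular supply (Section 4.2): "two bottles (6 month supply) of drug product dispensed to study subjects at the baseline study visit and at the 6 month visit". At 100 tablets a bottle this is 200 per kit and 400 in total.
- Extension: at most 42 pills (Section 5.3; Table 2, note 5).
- Month-12 remote visit: day 365 ± 14, so day 351 to 379 (Table 2).
- Collection limit: 16 × 7 = 112 days after the remote visit (Table 2, note 3).

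**The plan's own figure.** 6 weeks × 7 days × 1 tablet = 42 pills, so the stated equivalence is right. The share of the window left uncovered by these pills alone is (112 − 42)/112 = 70/112 = 62.5%.

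**Uncovered days at the limit** = latest assessment day − last covered day − 1. The documents do not say whether leftover kit tablets are kept, so three cases are shown.

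- A, no leftovers: the 42 pills start on the remote visit day, so the last covered day is visit day + 41.
- B, only the second kit is used, from day 182: 182 + 200 + 42 − 1 = day 423.
- C, every kit tablet is kept and used: 8 + 400 + 42 − 1 = day 449.

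| Remote visit | Latest assessment | A | B | C |
|---|---|---|---|---|
| Day 351 | Day 463 | 463 − 392 − 1 = 70 | 463 − 423 − 1 = 39 | 463 − 449 − 1 = 13 |
| Day 365 | Day 477 | 477 − 406 − 1 = 70 | 477 − 423 − 1 = 53 | 477 − 449 − 1 = 27 |
| Day 379 | Day 491 | 491 − 420 − 1 = 70 | 491 − 423 − 1 = 67 | 491 − 449 − 1 = 41 |

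No case covers the whole window. Section 5.3 counts the 16 weeks from the Visit 4 window and not from the remote visit. If that means the end of the window, the limit is day 379 + 112 = 491 for everyone, and case C gives 41 days throughout. If the optional extension is not sent, case C supply ends on day 407, and a day-365 remote visit leaves 477 − 407 − 1 = 69 days.

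**Primary endpoint.** The latest delayed Month-6 clinic walk is day 196 + 84 = 280 (Table 2, note 2, 12 weeks). A second kit started on day 182 lasts to 182 + 200 − 1 = day 381, so the gap does not arise there.

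**Week 54 call, case A, remote visit on day 365.** The last dose is on day 406 and the latest assessment on day 477. The call falls on day 484 to 487, which is 78 to 81 days after the last dose, against the 14 days in Section 9.6.3.

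**The case against.** The strongest reply is that this is a permissive pandemic provision. The drug may be mailed, the visit may be delayed, and both depend on when centers re-open. With the extension and leftover tablets, a day-365 remote visit is covered for (423 − 365 + 1)/7 = 8.4 weeks in case B or (449 − 365 + 1)/7 = 12.1 weeks in case C. Only late clinic visits fall outside. This stands: a reader might infer that 12-month values will be off drug, but the documents show only that they may be.

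A second reply is that the cap and the window do not formally contradict each other. One limits supply, the other limits data collection; treatment is planned for twelve months, and no section requires delayed assessments to be on drug. Taking a late value in preference to none is defensible. This also stands, but it leaves open what a late value labelled Month 12 represents, and the plan does not say.

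Third, much of the data is protected. The remote walk belongs to the visit window, the SF-36, emPHasis-10 and actigraphy stay with the remote visit, and a visiting service may draw blood. This narrows the exposure to echocardiography, the in-clinic walk, DXA and whatever blood is delayed. Remote walks need clearance and a companion, so not every subject will have one.

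Fourth, Section 5.3 says in general terms that drug is shipped when needed, and pill counts and withheld doses are recorded. The general line does not lift the specific 42-pill cap, and nothing requires the last dose to be dated against the assessment.

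A reader might also want a power figure. The 22 m difference, 80% power and 10% loss are six-month planning inputs. The documents give no SD, no 12-month power claim, no share of subjects affected and no offset time, so any such figure would be supposition.

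**Conclusion.** The point holds in a limited form. Under the stated cap and window, Month-12 clinic measurements after a remote visit may be taken when no supplied drug is left, and the analysis plan does not address this. At the 16-week limit, counted from the remote visit, the gap is 70 days with no leftovers and 13 to 41 days if every tablet is kept and used. For DXA it has no upper limit.

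These figures assume daily dosing as instructed and the full 42-pill extension. Dilution of the 12-month contrasts further requires that the effect wanes off treatment. Its size cannot be derived from the documents.

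The six-month primary endpoint, remote walks, questionnaires and actigraphy are outside the concern. A reader might also infer that on-drug values should become the main 12-month contrast. The documents do not support that: Sections 7.3.1, 7.3.5 and 9.6.5 commit to all randomized subjects and to follow-up after treatment stops, and selecting on drug status would remove their data.

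**What to change.** 1. Reconcile the supply cap with the assessment window in Section 5.3 and Table 2, including whether the 16 weeks run from the remote visit or from the Visit 4 window. Which figure should change is for the investigators. Reconcile the timing of the Week 54 call with the 14-day definition in Section 9.6.3 at the same time.
2. Record the date of last dose against the date of each delayed Month-12 assessment.
3. Keep all randomized subjects' values in the main intention-to-treat analysis. Before unblinding, pre-specify a sensitivity analysis of the 12-month endpoints restricted to values taken while on supplied drug. Check the remote-walk harmonization in the same way, using only pairs in which both walks were on drug.

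The cost is a protocol clarification, one more date on the case report form and a little analysis work. The restricted analysis will be less precise, and because it selects on a post-randomization event it should support the main result and not replace it. If the rule is left until after unblinding, any split by drug status will be post hoc.
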